13.5. Adherence to Assigned Treatment Performance Standard

The purpose of this performance standard is to identify the standard by which subjects are determined to be compliant with their assigned treatment during the study and how they will be handled in the analysis of study data.

Adherence to the assigned treatment is necessary to the integrity of the study analysis, which is dependent upon exposure to the assigned treatments. Compliance is determined by pill and syringe counts as described in [Section 5.3.5](#) and study treatment and concomitant medication dosing logs.

There are several performance standards for compliance for this study:

- < 80% compliant with the dosage regimen for any one of the orally administered study medications or have not used 2 or more injectable syringes expected to be used over the time between scheduled visits.
 - These subjects will be counseled and the site will implement appropriate measures to secure subject compliance, including instituting interim visits to evaluate and encourage compliance, as appropriate to the site and reason for non-compliance.
- < 70% compliant with the dosage regimen for any one of the orally administered study medications or have not used 2 or more injectable syringes expected to be used over the time between scheduled visits.
 - The reason for non-compliance with the dosing regimen should be documented in the dosing log of the subject's case report form, and should be reported as a protocol deviation and unless there is a protocol stipulated reason for non-compliance with the dosing regimen, this should be recorded as a dosing error.
- > 120% compliance with the dosing regimen for any one of the orally administered study medications or have not used 2 or more injectable syringes expected to be used over the time between scheduled visits.
 - The reason for non-compliance (more than expected consumption) with the dosing regimen should be documented in the dosing log of the subject's case

report form with the reason for non-compliance, reported as a protocol deviation, and recorded as a dosing error.

Subjects who are found to be <70% or >120% compliant with the dosage regimen for any one of the study medications at any time during the study will be censored from efficacy analyses utilizing the Per Protocol Analysis Set, but will be included in analyses utilizing the Full Analysis Set.

This study is being managed by an Alliance Partner. The Alliance Partner will have risk/mitigation plans in place to identify specific remedial actions to be taken, depending on the reason non-compliance with the dosing regimen; these actions will be implemented if the event exceeds the respective performance standard (CTPQS-106 Plan and Manage Study Execution, Version 3, Effective Date: 15-Feb-2013).

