5.3.5. Compliance

Compliance with expected consumption of dispensed medication will be assessed by determining the expected number of doses to be taken during any given time period and comparing that to the number of doses returned, keeping in mind that subjects may have their study drug temporarily withheld due to abnormal laboratory tests, adverse events, or the need to take a short course of a prohibited concomitant medication. Doses not taken during these events do not constitute protocol deviations and should not be considered dosing errors, but should be noted in the dosing log with the reason for reduced drug consumption.

Subjects, who are less than 80% compliant with the orally administered dosage regimen or have not used 2 or more injectable syringes expected to be used in the interval, will be counseled and the site will implement appropriate measures to secure subject compliance, including instituting interim visits to evaluate and encourage compliance, as appropriate to the site and reason for non-compliance.

When compliance of less than 70% of the expected number of doses for any one of the orally administered study medications or the subject has not used 3 or more injectable syringes that were expected to be used in the interval is suspected, the reason for non-compliance (more than or less than expected consumption) with the dosing regimen should be documented in the dosing log of the subject's case report form, and should be reported as a protocol deviation and unless there is a protocol stipulated reason for non-compliance with the dosing regimen, this should be recorded as a dosing error.

When compliance of more than 120% of the expected number of doses for the orally administered dosage regimen or have used 2 or more injectable syringes than was expected to be used in the interval, the reason for non-compliance (more than expected consumption) with the dosing regimen should be documented in the dosing log of the subject's case report form with the reason for non-compliance, reported as a protocol deviation, and recorded as a dosing error.

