- *An analysis by TNFi subset strata (ie, the sites/regions where either adalimumab or etanercept was used)* will be performed using Safety Analysis Set.
- The same analyses conducted based on Safety Analysis Set will be conducted using Per Protocol Analysis Set.

Unadjusted, or “crude” incidence rates by Total Time, 60-Day On-Treatment Time and 28-Day On-Treatment Time analysis will be calculated as well.

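### Protocol 5.3.5 and 13.5 contradict each other on injectable compliance, the 13.5 over-use rule is written backwards, and one syringe count means different compliance for adalimumab and etanercept

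*Protocol*

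**What the plan says.** **Protocol 5.3.5 (Compliance)** pairs each oral percentage with a syringe count.
- Below 80%: subjects who "have not used 2 or more injectable syringes expected to be used in the interval, will be counseled".
- Below 70%: a protocol deviation, and a dosing error unless the protocol gives a reason, when the subject "has not used 3 or more injectable syringes that were expected to be used in the interval".
- Above 120%: a deviation and dosing error for those who "have used 2 or more injectable syringes than was expected to be used in the interval".

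**Protocol 13.5 (Adherence to Assigned Treatment Performance Standard)** refers back to 5.3.5 for pill and syringe counts, then restates the tiers differently.
- Below 80%: two or more syringes unused, leading to counselling.
- Below 70%: "< 70% compliant with the dosage regimen for any one of the orally administered study medications or have not used 2 or more" injectable syringes, leading to a deviation.
- Above 120%: "> 120% compliance with the dosing regimen for any one of the orally administered study medications or have not used 2 or more" injectable syringes. The action under this bullet concerns consumption above what was expected.

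**Protocol 5.3.4 (Medication Errors)** has its own over-use rule. A deviation is reported for a doubled dose on one or more days, or for more than 120% of the prescribed dose over the visit interval. It has no syringe count.

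**Analysis sets.** Protocol 13.5 says of "Subjects who are found to be <70% or >120% compliant with the dosage regimen for any one of the study medications at any time" that they are censored from efficacy analyses on the Per Protocol set. SAP 8.2.3 runs all efficacy analyses on the Full Analysis Set. SAP 5.2 defines the Per Protocol set through the potentially important protocol deviation (pIPD) process and gives no compliance limit. For the co-primary safety endpoints, SAP 8.2.1 states: "The same analyses conducted based on Safety Analysis Set will be conducted using Per Protocol Analysis Set".

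**The concern.** A site or monitor following 13.5 would log a deviation that 5.3.5 does not call for, and would record missed injections as over-consumption. A fixed syringe count also cannot stand in for one percentage when one comparator is injected every other week and the other weekly. The oral arms are judged in percent and the TNFi arm by count, so the same degree of non-compliance can be a deviation in one arm and not in another. The comparator depends on country (adalimumab in the US, Puerto Rico and Canada, etanercept elsewhere), so the discrepancy also runs along the regional strata that SAP 8.2.1 uses as a consistency check.

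At stake is whether compliance deviations can be compared across arms. Beyond that, SAP 5.5 says the pIPD list is built in line with the protocol's requirements, and here the protocol offers no single rule. If compliance deviations are treated as pIPDs that could affect the analysis, the Per Protocol rerun of the safety analyses would carry the inconsistency.

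**Working it through.** The documents give no derivation of the syringe counts, so there is no plan figure to reproduce. The check has three parts.

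**1. The sections side by side**

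| Tier | 5.3.5 syringe trigger | 13.5 syringe trigger |
|---|---|---|
| Below 80% (counsel) | 2 or more unused | 2 or more unused |
| Below 70% (deviation) | 3 or more unused | 2 or more unused |
| Above 120% (deviation) | 2 or more extra | 2 or more unused |

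In 13.5 all three tiers have the same syringe trigger. Counselling and deviation cannot be told apart for injectables, and no syringe count there detects over-use.

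**2. What a count means in percent**

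Inputs:
- Adalimumab is one syringe every two weeks and etanercept one per week (Protocol 3).
- The regular visit interval is three months; the target days in SAP Appendix 1.1 step by 90 days, and 90/7 = 12.9 weeks.
- I take 13 weeks, with 12 to 14 as the range.

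Expected syringes are 13/2 = 6.5 for adalimumab (6 to 7) and 13/1 = 13 for etanercept (12 to 14). Compliance is 1 − missed/expected, or 1 + extra/expected.

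| Count | Adalimumab | Etanercept |
|---|---|---|
| 2 missed | 1 − 2/6.5 = 69.2% (66.7 to 71.4) | 1 − 2/13 = 84.6% (83.3 to 85.7) |
| 3 missed | 1 − 3/6.5 = 53.8% (50.0 to 57.1) | 1 − 3/13 = 76.9% (75.0 to 78.6) |
| 2 extra | 1 + 2/6.5 = 130.8% (128.6 to 133.3) | 1 + 2/13 = 115.4% (114.3 to 116.7) |

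Against an oral subject, who becomes a deviation only below 70% or above 120%:
- Under 13.5, an etanercept subject at about 85% is a deviation.
- Under 5.3.5, an etanercept subject is a deviation at about 77%. An adalimumab subject at about 69% is not; the next whole syringe takes that subject to about 54%.
- Two extra etanercept syringes (about 115%) are a deviation under 5.3.5 but do not meet the 120% criterion in 5.3.4.

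**3. Could one count serve both comparators?**

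The smallest whole count that crosses each oral limit over 13 weeks is:
- Below 80%: more than 0.2 × 6.5 = 1.3, so 2 (adalimumab); more than 0.2 × 13 = 2.6, so 3 (etanercept).
- Below 70%: more than 0.3 × 6.5 = 1.95, so 2; more than 0.3 × 13 = 3.9, so 4. With 7 and 14 syringes expected, these become 3 and 5.
- Above 120%: 2 extra; 3 extra.

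No single count matches the oral limit for both comparators in any tier. This shows only that the counts are not equivalent; it does not say which limit is right.

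**The case against.** The strongest reply is that these are drafting slips in an operational section. Section 13 describes itself as an overview of a fuller Performance Standard Document, and 13.5 defers to 5.3.5. Injectable over-use is caught in 5.3.5 and again in 5.3.4, so the reversed bullet need not let it go unreported. One syringe trigger is easy for sites to apply, and its mapping to different percentages is a simplification rather than a contradiction. Protocol 5.3.5 also exempts doses withheld for laboratory results, adverse events or short courses of prohibited drugs. Most of this stands as a limit on the consequences. It does not remove the conflict: a reader of the protocol cannot tell whether two or three unused syringes make a deviation, and 13.5 states the wrong direction for over-use.

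A reader might go further and infer that the Per Protocol set is already defined differently by arm, and so biases the check supporting the non-inferiority conclusions. The documents do not support that. The only explicit compliance exclusion is in percent, and it concerns Per Protocol efficacy analyses that the SAP does not run. The safety Per Protocol set depends on the pIPD list, which is not in these documents, and no passage says that a syringe-count deviation belongs on it.

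A reader might also infer from the at-any-time wording that a large share of subjects would be excluded. The documents give no rate of out-of-range intervals, so that share cannot be calculated.

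**Conclusion.** The contradictions are plain in the text. Two and three unused syringes are both given for the below-70% deviation tier, and the above-120% tier in 13.5 is reversed. The lack of equivalence between comparators is also real: 69% against 85% for two missed, 54% against 77% for three, and 131% against 115% for two extra. These figures assume a regular interval of about 13 weeks, and the ordering holds from 12 to 14 weeks. Deviation reporting therefore differs between oral and injectable arms and between adalimumab and etanercept regions.

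Unequal Per Protocol exclusion by arm is a risk, conditional on these deviations becoming pIPDs judged able to affect the analysis. The primary hazard ratios and the 1.8 and 2.0 decision rules rest on the Safety Analysis Set and are unaffected. The correction is worth making because it is cheap and the rule is wrong as written, not because the main result is in doubt.

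**What to change.** 1. Merge the compliance rules of Protocol 5.3.4, 5.3.5 and 13.5 into one table that the other sections cite. The sponsor chooses the thresholds. Correct the above-120% bullet in 13.5 so that its trigger and action point the same way.
2. Express any compliance limit used for deviations or analysis sets as a percentage of expected doses, so that it means the same for tofacitinib, adalimumab and etanercept. A syringe count can remain as a site prompt if it is given separately for each comparator.
3. State in SAP 5.2, before the exclusion list is finalized ahead of database release, whether and how compliance enters the Per Protocol set used for the safety endpoints. Either drop the 13.5 reference to Per Protocol efficacy analyses or align it with SAP 8.2.3.

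The cost is protocol and SAP wording, plus a derivation from drug-accountability data already collected. No new data are needed and the primary analysis does not change.

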13.6. Cross-Ins Performance Standard

Subjects will either remain in their respective assigned treatment (tofacitinib 5 mg BID, tofacitinib 10 mg BID, adalimumab 40 mg QOW or etanercept 50 mg weekly) or be identified as being switched to standard of care, which may include tofacitinib, adalimumab or etanercept if those compounds are standard of care in their locality. Therefore, a performance standard for Cross-Ins is not relevant to this study.

13.7. Subject Retention Performance Standard

The purpose of this performance standard is to identify subject retention performance standards and to define the actions to be taken if the performance standard is not met.

The performance standard for subject retention within their assigned treatment group is an assigned treatment discontinuation rate of approximately 15% annually during the conduct of the study with higher discontinuation rates seen during the first year of the study.

The expected assigned treatment discontinuation rates were developed from overall discontinuation rates seen in tofacitinib RA Phase 2/3 studies and the Long-Term Extension Studies and have been applied to this study as the projected performance standard for subject retention within their assigned treatment group.

Discontinuation rates, including reason for discontinuation, are collected and reviewed by the study clinician periodically during the study. Discontinuation rates will be evaluated at least monthly for trends in total rates and components of these rates (eg, adverse events, insufficient clinical response, no longer willing to participate).

This study is being managed by an Alliance Partner. The Alliance Partner will have risk/mitigation plans in place to identify specific remedial actions to be taken, depending on the reason for the increased rate in discontinuation; these actions will be implemented if the rate of discontinuation exceeds the performance standard. However, intermediate interventions may be applied if component rates are trending upwards and reasons can be identified and addressed by the study team (eg, inappropriate subject selection, retraining of

sites, etc) (CTPQS-106 Plan and Manage Study Execution, Version 3, Effective Date: 15-Feb-2013).

13.8. Timeliness of Data Performance Standard

The purpose of this performance standard is to evaluate timeliness of data entry and define actions to be taken if the performance standard is not met.

The performance standard for timeliness of data entry is compliance to the requirement that investigators complete data entry into the case report form (CRF) within four (4) calendar days of that data becoming available.

This study is being managed by an Alliance Partner. The Alliance Partner will have a process in place to monitor timely CRF data entry that includes monthly monitor review of investigator performance to data entry timelines and a structured action plan and escalation/communication process triggered by site performance with data entry timelines (CTPQS-113 Study Site Initiation, Monitoring and Closure, Version 5, Effective Date: 15-Feb-2013).

14. DEFINITION OF END OF TRIAL

14.1. End of Trial in a Member State

End of Trial in a Member State of the European Union is defined as the time at which it is deemed that sufficient subjects have been recruited and completed the study as stated in the regulatory application (ie, Clinical Trial Application (CTA)) and ethics application in the Member State. Poor recruitment (recruiting less than the anticipated number in the CTA) by a Member State is not a reason for premature termination but is considered a normal conclusion to the study in that Member State.

14.2. End of Trial in all Other Participating

End of Trial in all other participating countries is defined as that time when sufficient subjects have been recruited and completed the study (or the study is prematurely terminated by the Sponsor) and the database has been locked for the final study analysis.

15. SPONSOR DISCONTINUATION CRITERIA

Premature termination of this study may occur because of a regulatory authority decision, change in opinion of the IRB/IEC, drug safety problems, a recommendation by the DMC, a recommendation by the Steering Committee, or at the discretion of Pfizer. In addition, Pfizer retains the right to discontinue development of tofacitinib for use in patients with rheumatoid arthritis at any time.

If a study is prematurely terminated or discontinued, Pfizer will promptly notify the investigator. After notification, the investigator must contact all participating subjects and the hospital pharmacy (if applicable) within one week. As directed by Pfizer, all study materials must be collected and all CRFs completed to the greatest extent possible.

16. PUBLICATION OF STUDY RESULTS

16.1. Communication of Results by Pfizer

Pfizer fulfills its commitment to publicly disclose clinical trial results through posting the results of studies on www.clinicaltrials.gov (ClinicalTrials.gov). Pfizer registers study protocols and posts Basic Results on ClinicalTrials.gov for Pfizer-sponsored interventional studies in human subjects that evaluate the safety and/or efficacy of a Pfizer product.

The results are posted in a tabular format called Basic Results.

For studies involving a Pfizer product, the timing of the posting depends on whether the Pfizer product is approved for marketing in any country at the time the study is completed:

- For studies involving products applicable under the US Food and Drug Administration Amendments Act of 2007 (FDAAA), ie, FDA-approved products, Pfizer posts results within one year of the primary completion date (PCD). For studies involving products approved in any country, but not FDA approved, Pfizer posts results one year from last subject, last visit (LSLV);
- For studies involving products that are not yet approved in any country, Pfizer posts the results of already-completed studies within 30 days of US regulatory approval, or one year after the first ex-US regulatory approval of the product (if only submitted for approval ex-US);
- For studies involving products whose drug development is discontinued before approval, Pfizer posts the results within one year of discontinuation of the program (if there are no plans for outlicensing or within two years if outlicensing plans have not completed).

Primary Completion Date is defined as the date that the final subject was examined or received an intervention for the purposes of final collection of data for the primary outcome, whether the clinical trial concluded according to the pre-specified protocol or was terminated.

16.2. Publications by Investigators

Pfizer has no objection to publication by Investigator of any information collected or generated by Investigator, whether or not the results are favorable to the Investigational Drug. However, to ensure against inadvertent disclosure of Confidential Information or unprotected Inventions, Investigator will provide Pfizer an opportunity to review any proposed publication or other type of disclosure before it is submitted or otherwise disclosed.

Investigator will provide manuscripts, abstracts, or the full text of any other intended disclosure (poster presentation, invited speaker or guest lecturer presentation, etc.) to Pfizer at least 30 days before they are submitted for publication or otherwise disclosed. If any patent action is required to protect intellectual property rights, Investigator agrees to delay the disclosure for a period not to exceed an additional 60 days.

Investigator will, on request, remove any previously undisclosed Confidential Information (other than the Study results themselves) before disclosure.

If the Study is part of a multi-centre study, Investigator agrees that the first publication is to be a joint publication covering all centers. However, if a joint manuscript has not been submitted for publication within 12 months of completion or termination of the Study at all participating sites, Investigator is free to publish separately, subject to the other requirements of this Section.

For all publications relating to the Study, Institution will comply with recognized ethical standards concerning publications and authorship, including Section II - “Ethical Considerations in the Conduct and Reporting of Research” of the Uniform Requirements for Manuscripts Submitted to Biomedical Journals, <http://www.icmje.org/index.html#authorship>, established by the International Committee of Medical Journal Editors.

Publication of study results is also provided for in the Clinical Study Agreement between Pfizer and the institution. In this section entitled [Publications by Investigators](#), the defined terms shall have the meanings given to them in the Clinical Study Agreement.

Appendix 1. The 2010 American College of Rheumatology/European League Against Rheumatism Classification Criteria for Rheumatoid Arthritis¹⁶

	Score
Target population (Who should be tested?): Patients who	
1. Have at least 1 joint with definite clinical synovitis (swelling)*	
2. With the synovitis not better explained by another disease†	
Classification criteria for RA (score-based algorithm: add score of categories A-D; a score of $\geq 6/10$ is needed for classification of a patient as having definite RA)‡	
Joint involvement§	
1 large joint¶	0
2-10 large joints	1
1-3 small joints (with or without involvement of large joints)#	2
4-10 small joints (with or without involvement of large joints)	3
>10 joints (at least 1 small joint)**	5
Serology (at least 1 test result is needed for classification)††	
Negative RF and negative ACPA	0
Low-positive RF or low-positive ACPA	2
High-positive RF or high-positive ACPA	3
Acute-phase reactants (at least 1 test result is needed for classification)‡‡	
Normal CRP and normal ESR	0
Abnormal CRP or abnormal ESR	1
Duration of symptoms§§	
<6 weeks	0
≥ 6 weeks	1

*The criteria are aimed at classification of newly presenting patients. In addition, patients with erosive disease typical of rheumatoid arthritis (RA) with a history compatible with prior fulfillment of the 2010 criteria should be classified as having RA. Patients with longstanding disease, including those whose disease is inactive (with or without treatment) who, based on retrospectively available data, have previously fulfilled the 2010 criteria should be classified as having RA.
†Differential diagnoses vary among patients with different presentations, but may include conditions such as systemic lupus erythematosus, psoriatic arthritis, and gout. If it is unclear about the relevant differential diagnoses to consider an expert rheumatologist should be consulted.
‡Although patients with a score of $< 6/10$ are not classifiable as having RA, their status can be reassessed and the criteria might be fulfilled cumulatively over time.
§Joint involvement refers to any *swollen* or *tender* joint on examination, which may be confirmed by imaging evidence of synovitis. Distal interphalangeal joints, first carpometacarpal joints, and first metatarsophalangeal joints are *excluded from assessment*. Categories of joint distribution are classified according to the location and number of involved joints, with placement into the highest category possible based on the pattern of joint involvement.
¶“Large joints” refers to shoulders, elbows, hips, knees, and ankles.

#“Small joints” refers to the metacarpophalangeal joints, proximal interphalangeal joints, second through fifth metatarsophalangeal joints, thumb interphalangeal joints, and wrists.

**In this category, at least 1 of the involved joints must be a small joint; the other joints can include any combination of large and additional small joints, as well as other joints not specifically listed elsewhere (eg., temporomandibular, acromioclavicular, sternoclavicular, etc.).

†† Negative refers to IU values that are less than or equal to the upper limit of normal (ULN) for the laboratory and assay; low-positive refers to IU values that are higher than the ULN but ≤ 3 times the ULN for the laboratory and assay; high-positive refers to IU values that are >3 times the ULN for the laboratory and assay. Where rheumatoid factor (RF) information is only available as positive or negative, a positive result should be scored as low-positive for RF. ACPA = anti-citrullinated protein antibody.

‡‡ Normal/abnormal is determined by local laboratory standards. CRP = C-reactive protein; ESR = erythrocyte sedimentation rate.

§§ Duration of symptoms refers to patient self-report of the duration of signs or symptoms of synovitis (eg, pain, swelling, tenderness) of joints that are clinically involved at the time of assessment, regardless of treatment status.

